STATISTICAL CONSIDERATIONS	Estimated average acute care utilization rate for EA-SCD is 6 visits / year. This study is designed to detect a 20% reduction in the number of acute care encounters per year which is considered clinically significant to our patient stakeholders. Based on a two- sided alpha = 0.05 significance level, 67 subjects per arm would provide approximately 85% power to detect a 20% reduction in the number of acute care utilizations under individual randomization, assuming the number of encounters follows a Poisson distribution for rare events. Sample size was inflated based on the cluster size coefficient of variation among our 14 participating clinical sites (55%) and the intra-class correlation (ICC) assumed to be 0.05. Based on these parameters, 183 subjects per arm (366 total subjects) will retain approximately 85% power. The sample size was increased to 537 total EA-SCD subjects to account for potential missing data and allow for robust evaluation of secondary endpoints. It is estimated that this can be accomplished with an enrollment rate of 35% of the EA-SCD patient population.
NUMBER OF EA-SCD PARTICIPANTS	537 total participants will be enrolled Each arm will enroll approximately 269 EA-SCD aged 16 – 25 years
NUMBER OF CLUSTERS	There will be 14 cluster sites, each cluster site comprised of a pediatric SCD clinic, an adult SCD clinic and a SCD CBO. There are 8 large cluster sites with ≥40 EA-SCD currently in pediatrics and 6 small cluster sites with <40 EA-SCD currently in pediatric care. Based on self-reported enrollment targets from each site, 80% of participants will come from large clusters.

SCHEMA

[figure not shown]
Study Schema Figure 1: Overview of Study Design

	Study Schema										
Practices with Emerging Adults with SCD (EA-SCD) aged 16 - 25y Randomized at the Practice Level											
Small Sized Program [≤ 40 EA-SCD] Large Sized Program [> 40 EA-SCD]											
Arm 1- A	Arm 1- B	Arm 2-A	Arm 2-B								
Structured Education Based Transition Program [STE]	Structured Education Based Transition Program [STE] + Peer Mentoring [STE + PM]	Structured Education Based Transition Program [STE]	Structured Education Based Transition Program [STE] + Peer Mentoring [STE + PM]								
	Outcome Meas	ures at 24 Montl	ns								
Primary Outcome: Cha		are visits [ED visits, Adm Hospital Days]	issions, Readmissions at 14d,								

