10.2 Sample Size and Accrual

Sample size calculations are based on the primary endpoint of acute care utilization visits per year (at the EA-SCD participant level). Utilizing a randomized cluster design, seven clinical sites will be randomized per arm. The sample size calculation strategy is to calculate the required minimum sample size based on an individual patient randomized design, and then inflate the sample size based on cluster randomized considerations.⁵⁴ A conservative estimate of the average acute care utilization rate for EA-SCD is 6 acute care visits per year based on data for North Carolina reported by the RuSH population surveillance project.⁴ In South Carolina, the acute care utilization rates among 18-30 y with SCD was reported as 7.17 (95% CI 6.34-7.99).55 At Atrium Health (formerly known as Carolinas Healthcare System), 295 EA-SCD had 1972 emergency department visits and 221 hospital admissions in 2015 with an average acute care

utilization rate of 6.82 visits per year. This study is designed to detect a 20% reduction in the number of acute care encounters per year (assuming a base case of 6 encounters). A 20% reduction in acute care utilization is considered clinically significant based on patient partners reporting that 1 less acute care visit a year is meaningful. Based on a two- sided alpha = 0.05significance level, 67 EA-SCD participants per arm would provide approximately 85% power to detect a 20% reduction in the number of acute care utilizations under individual randomization, assuming the number of encounters follows a Poisson distribution for rare events. The sample size will be inflated based on two parameters: the cluster size coefficient of variation and the intra-class correlation (ICC).⁵⁴ The cluster size coefficient of variation observed among the 14 participating clinical sites is 55%. Therefore, the coefficient of variation is assumed to be 60% and the ICC is assumed to be 0.05.⁵⁶ Based on these parameters, a minimum of 183 EA-SCD participants per arm (366 total EA-SCD participants) will retain approximately 85% power. To account for potential missing data and allow for robust evaluation of secondary endpoints the sample size will be increased to a total of 537 EA-SCD participants. It is estimated that this enrollment can be accomplished with an enrollment rate of 35% of the EA-SCD patient population.

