10.5.4 Primary Analysis

To evaluate the impact of PM, the acute care utilization rate per year will be compared between the PM+STE and STE arms. This will be accomplished using generalized linear mixed model with a Poisson distribution-log link construct. The model will include fixed effects for baseline acute care visits per year, the stratification factor (large sites vs small sites) and treatment arm, and a random effect for clinical site. Corresponding 95% confidence intervals will be calculated for the estimated ACU rate in each treatment arm.

Supportive and sensitivity analyses will be conducted to include potential confounding factors such as urban versus rural sites, education level, older first degree relative with SCD, genotype, age at transfer to adult care, and type of receiving provider (primary versus specialty). Univariate models will be fit for each factor, and those identified to be individually prognostic will be included in a multivariable model, and backward elimination followed by forward selection will be used to identify factors that are independently prognostic and to establish a final base model. Finally, treatment arm will be added to the base model to evaluate the impact of the intervention adjusting for significant baseline factors.

Two analyses will be conducted to estimate the impact of differential accrual between arms over time: (1) An additional term of year of enrollment will be added to the GLMM as a categorical variable; (2) We will subset the analyses to EA-SCD who were contemporaneously enrolled. Comparison of the PM+STE and STE ACU estimates from this subset to those results including all enrolled with and without controlling for year of enrollment will provide a comprehensive assessment of the potential bias due to differential accrual between arms over time. ACU rate in the STE only arm will be compared to historical ACU rates which were used for the original power calculations. Although these are comparisons to historical controls, this will provide preliminary evidence using a robust sample size of the potential impact of the structure transition education.

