10.5.5 Secondary Analysis

EA-SCD PRO's will be analyzed quantitatively using linear mixed models for repeated measures. The models will include fixed factors for baseline scales, the site size stratification factor, treatment arm, assessment time point, and the treatment arm by time point interaction. Random factors will include investigational site and subject within site to account for correlation in responses within individual sites and within the same subject. Model-based estimates of PRO scores will be used to estimate percentage change between the treatment arms. Additionally, PRO will be analyzed using survival analysis techniques. For each EA-SCD participant, the time from baseline to a 10% worsening (TTW) in the scale will be calculated. For EA-SCD participants not experiencing a 10% worsening, TTW will be censored at the last patient reported outcome assessment. TTW will be analyzed using Kaplan-Meier techniques and Cox proportional hazards models. The

proportional hazards models will include the same factors as described for the primary analysis. Planned sensitivity analysis will be conducted to evaluate time to worsening for worsening thresholds ranging from 10% to 30%. The repeated measures and survival analyses of the EA-SCD PRO's will also include supportive and sensitivity analyses to account for potential baseline confounders as previously described in the primary analysis. EA-SCD satisfaction with transition services will be summarized descriptively.

Intervention fidelity will be analyzed descriptively. A CONSORT-type diagram will be provided, including a summary of all mentors who consented, had a background check, passed the background check, completed practice call 1, completed Peer Mentor University online training, completed practice call 2, and were matched with at least one EA-SCD. Timelines for mentors and EA-SCDs on the PM arm will be summarized descriptively. Frequency of mentor contacts will be analyzed descriptively in terms expected contacts per protocol versus actual. This will include calls placed (mentor to EA-SCD), calls answered (EA-SCD to mentor), messages sent (mentor to EA-SCD), and messages received (EA-SCD to mentor).

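### Supportive models choose covariates from the outcome data with arm left out: a slight pull toward zero, and an adjustment set not fixed in advance

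*Combined protocol and SAP*

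**What the plan says.** Section 10.5.4 of the combined protocol and SAP fixes the primary model in advance: a Poisson log-link mixed model with baseline acute care visits, the site-size stratum, arm and a random site effect. No selection touches it.

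The supportive and sensitivity analyses in the same section work differently. Six possible confounders are named, as examples rather than a closed list: urban or rural site, education, an older first-degree relative with SCD, genotype, age at transfer, and whether the receiving provider is primary care or specialty. Then:

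- "Univariate models will be fit for each factor, and those identified to be individually prognostic will be included in a multivariable model"
- "backward elimination followed by forward selection will be used to identify factors that are independently prognostic"
- "Finally, treatment arm will be added to the base model"

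No threshold is given for any step. The text does not say whether site size and baseline visits are held in the base model, offered for selection or left out. Section 10.5.5 carries the procedure over: the PRO repeated-measures and survival analyses "will also include supportive and sensitivity analyses to account for potential baseline confounders as previously described in the primary analysis". The main models in 10.5.5 have their terms fixed in advance.

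**The concern.** The stated aim is to address confounding, but selection on outcome p-values looks for prognostic factors. With arm absent, a factor that happens to line up with arm can look prognostic because it carries part of the arm effect. With seven sites per arm, such alignment is likely for a site-level factor. It is most often selected when chance site variation adds to the borrowed arm effect. When arm enters last, the factor keeps some of what belongs to arm, so the arm estimate moves toward zero. With no true effect there is nothing to borrow, and no bias is expected.

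These models are meant to show that the primary result is robust. That is hard to argue if the outcome data choose the adjustment set and the stratification factor is not guaranteed a place in it. Section 10.5.6 adds a practical problem: complete-case results are to be compared with multiply imputed ones, and nothing says how selection runs across imputations. The two sets of results could adjust for different covariates.

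**Working it through.** **1. The plan's design figures reproduce.** The synopsis says "Based on a two- sided alpha = 0.05 significance level, 67 subjects per arm would provide approximately 85% power". Section 10.2 gives the rest: "This study is designed to detect a 20% reduction", "assuming a base case of 6 encounters", and "the coefficient of variation is assumed to be 60% and the ICC is assumed to be 0.05", with seven sites per arm.

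- Individual randomization: n = (1.960 + 1.036)² × (6 + 4.8) / (6 − 4.8)² = 8.98 × 10.8 / 1.44 = 67.3. Power at 67 per arm is 84.8%.
- Clustering: N = n[1 + ((1 + CV²)N/k − 1) × ICC] with k = 7. Solved for N: 67 × 0.95 / (1 − 67 × 0.05 × 1.36 / 7) = 63.65 / 0.3491 = 182.3, so 183 per arm, as stated.

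**2. Simulation of the supportive procedure.** There were 3,000 trials per scenario.

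From the documents: 14 sites (8 large, 6 small), about 80% of 537 participants in large sites, arm randomized within size stratum, and a true rate ratio of 0.80 (log −0.2231).

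Assumed: covariate prevalences and effects, one-year counts, urban/rural as a site-level factor, site size offered as a seventh candidate, baseline visits omitted, and selection at p < 0.05 or p < 0.20. Two variance settings were used:

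- Poisson: site log-variance from ICC 0.05, (0.05/0.95) × 6/6² = 0.0088.
- Overdispersed: site log-variance 0.10 and patient-level gamma variance 1.5, guided by the 5.3 ± 8.5 visits per year in section 1.1.

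The shift is the paired difference between the planned procedure and a model with all seven factors (Monte Carlo standard error 0.0003 to 0.0013).

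| Setting | Site-size RR | Urban RR | p | Planned, log RR | All factors, log RR | Shift | Shift / 0.2231 | Site size kept |
|---|---|---|---|---|---|---|---|---|
| Poisson | 1.0 | 1.0 | 0.05 | −0.2208 | −0.2237 | 0.0029 | 1.3% | 1.5% |
| Poisson | 1.2 | 1.0 | 0.05 | −0.2200 | −0.2236 | 0.0036 | 1.6% | 47.6% |
| Poisson | 1.5 | 1.0 | 0.05 | −0.2212 | −0.2225 | 0.0013 | 0.6% | 99.5% |
| Poisson | 1.2 | 1.2 | 0.05 | −0.2110 | −0.2239 | 0.0129 | 5.8% | 38.8% |
| Overdispersed | 1.0 | 1.0 | 0.05 | −0.2186 | −0.2230 | 0.0044 | 2.0% | 9.2% |
| Overdispersed | 1.2 | 1.0 | 0.05 | −0.2174 | −0.2234 | 0.0060 | 2.7% | 19.2% |
| Overdispersed | 1.5 | 1.0 | 0.05 | −0.2173 | −0.2237 | 0.0064 | 2.9% | 48.7% |
| Poisson | 1.2 | 1.0 | 0.20 | −0.2192 | −0.2236 | 0.0043 | 1.9% | 77.1% |
| Overdispersed | 1.0 | 1.0 | 0.20 | −0.2149 | −0.2230 | 0.0081 | 3.6% | 23.9% |
| Poisson, no arm effect | 1.2 | 1.0 | 0.05 | 0.0007 | 0.0011 | −0.0004 | n/a | 72.6% |

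As rate ratios, the planned procedure averages 0.802 to 0.810 against 0.80. Keeping arm in at every selection step, and site size in the final model, gives 0.799 to 0.801.

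**3. Where the shift comes from.** With p < 0.05 and a true arm effect, a pure-noise urban/rural factor was retained in 3% to 9% of trials. In those trials the mean log rate ratio was −0.180 to −0.197, a rate ratio of about 0.82 to 0.84.

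**4. Factors arising after enrollment.** Under sections 1.2 and 3.2.1, participants enroll in pediatrics with transfer planned 6 to 12 months after consent. Age at transfer and receiving provider are therefore not known at enrollment, although 10.5.4 describes the selected factors as baseline. In one Poisson scenario where arm shifted provider type, a model without that factor gave −0.2760 (rate ratio 0.759, the total effect). The planned procedure gave −0.2188 (0.804), and all named factors together gave −0.2227 (0.800). The loss under the planned procedure is 0.2760 − 0.2188 = 0.0572, about 21% of the total log effect. Keeping arm in during selection did not correct it (0.800).

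**The case against.** The strongest reply is that no main analysis is touched, the shift is small and toward no effect, and choosing prognostic factors without looking at arm stops anyone from picking covariates that flatter the intervention. The first two points stand and limit the weight of this one. The third is a fair reason not to select on the arm estimate, but a list fixed in advance gives the same protection without the pull toward zero.

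Three stronger readings are tempting and are not supported.

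- A reader might infer that the site-size stratum will usually be dropped. The documents neither name it as a candidate nor say it is removed, and 10.5.4 can be read as adding factors to the primary model. When it was assumed to be a candidate, the drop rate at p < 0.05 with a true arm effect ran from 0.5% to 98.5%, depending on inputs the documents do not give. What can be said is that its retention is not stated.
- A reader might infer that the trial's main conclusions are biased. They rest on models with prespecified terms.
- A reader might conclude that every named factor should simply be forced in. Two arise after enrollment, so adjusting for them can remove part of the arm effect. Because multivariable models are complete-case (10.5.6), it could also drop participants who never transferred.

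**Conclusion.** The point holds for the supportive and sensitivity models only. If mentoring works, the adjusted estimate is pulled toward zero by about 1% to 6% of the log rate ratio, mainly through site-level factors aligned with arm by chance across 14 sites. Under the null there is no pull. These sizes rest on assumed covariate effects and thresholds, and on site size being a candidate. Where site size was almost always retained (99.5% of trials), the shift was 0.6%.

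The more lasting weakness does not depend on the simulation. The adjustment set is chosen from the outcome data, no threshold is stated, and neither site size nor baseline visits is guaranteed a place. The change is worth making because it is nearly free, not because the bias is large.

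**What to change.** Replace the selection text in 10.5.4 with a fixed model containing:

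- the primary-model terms: baseline visits (baseline score for PROs), site size, arm and the random site effect; and
- a closed list of factors fixed at enrollment: urban/rural, education level, older first-degree relative with SCD, and genotype.

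Enter all of them together, with no screening or stepwise steps. Use the same set for the supportive PRO and time-to-worsening models in 10.5.5. Take age at transfer and type of receiving provider out of this set, and report any model containing them separately as exploratory. Section 10.5.7 refers back to this list for its subgroup factors, so check that cross-reference.

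The cost is SAP wording, a few more model terms and some complete-case loss. The multiple imputation of baseline covariates already planned in 10.5.6 addresses that loss, and with a fixed set the imputed and complete-case results adjust for the same factors.

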specialized and primary - during transition, amplifying existing barriers to accessing crucial services as disease burden is increasing. 20,21 A retrospective study showed that patients who are transitioning received 46% fewer transfusions by age 22y compared to children and were 4.7 times less likely to receive iron chelation by age 25y. 21 At Atrium Health (formerly known as Carolinas Healthcare System), a large healthcare system in the SE US that provides care for 1300 adults and 400 children with SCD, only 8-14% of EA-SCD accessed a scheduled visit with their primary care/SCD provider in 2015 with mean acute care reliance (ACR; number of acute care visits per year/ [all acute care visits + all ambulatory care visits]) rates of 42% (Fig 2). Mean acute care visits/year rose significantly from 2.1 ± 2.9 among 16- 18y to 4.2 ± 6.8 among 19 - 21y and was highest among 21 - 25y at 5.3 ± 8.5 (p<0.01). ACR (\geq 0.33) is an indicator of inadequate access to primary and preventative care. 22 EA-SCD report having inadequate information about adult care and a poor understanding of their disease and how it becomes more complex with age. $^{14, 16}$ There are significant knowledge gaps and poor communication between pediatric and adult providers that worsen the problem created by a lack of standardized EA-SCD patient education curriculum.

Limited evidence on effective transition programming:

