10.5.3 Baseline Subject Characteristics

A summary of EA-SCD participant demographics, disease characteristics, and acute/ambulatory care utilization in the 12 months prior to enrollment will be assessed.

A summary of mentor/advisor demographics and disease characteristics will also be completed.

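### The historical comparison of the STE arm cannot isolate an effect of structured education: with no effect at all, the protocol's own rates imply anything from a large apparent benefit to a large apparent harm

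*Combined protocol and SAP*

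**What the plan says.** The Primary Analysis section (10.5.4) adds a non-randomised comparison to the randomised one: "ACU rate in the STE only arm will be compared to historical ACU rates which were used for the original power calculations". It then interprets it: "Although these are comparisons to historical controls, this will provide preliminary evidence using a robust sample size of the potential impact" of the education programme. The section gives no age standardisation, no common visit definition and no adjustment for period or region. It speaks of rates in the plural without saying which one is the comparator.

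Section 10.2 gives three candidates:

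- The base case: "A conservative estimate of the average acute care utilization rate for EA-SCD is 6 acute care visits per year", from North Carolina surveillance (reference 4).
- South Carolina: "the acute care utilization rates among 18-30 y with SCD was reported as 7.17".
- The lead health system: "295 EA-SCD had 1972 emergency department visits and 221 hospital admissions in 2015", with a stated average "utilization rate of 6.82 visits per year".

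The Background (1.1) gives age-specific rates. For the lead system: "Mean acute care visits/year rose significantly from 2.1 ± 2.9 among 16- 18y to 4.2 ± 6.8 among 19 - 21y", and 5.3 in the oldest band (21-25). It also gives 2.04 (10-17 years) and 3.61 (18-30 years) for eight states, 0.8 (10-19) and 3.0 (20-49) for Georgia, and 5 (under 18) and 12 (18-35) for North Carolina, the last also from reference 4.

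Participants are 16 to 25 and in a pediatric programme at consent (3.2.1). They spend 6 to 12 months there (1.2) and are then followed for at least 24 months in adult care (5). For the year before enrolment, "acute/ambulatory care utilization in the 12 months prior to enrollment will be assessed" (10.5.3).

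**The concern.** A single-arm comparison with an external rate is informative only if the external rate is what the arm would have shown without the programme. Here acute care use changes steeply with age and at transfer to adult care, differs several-fold between states, and depends on which visits are counted. None of these is controlled. The plan's acknowledgement that these are historical controls corrects nothing, and a large sample only narrows the interval around a confounded difference.

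The stakes are what the trial may say about structured education, which both arms receive and which therefore has no randomised control. The synopsis says the mentoring comparator can no longer be assessed quantitatively as planned, so the historical comparison could receive more weight in the report than its design supports.

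**Working it through.** **1. Which historical rate drove the power calculation.** With 6 versus 4.8 visits per year, two-sided alpha 0.05 and 85% power:

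n = (1.960 + 1.036)² × (6 + 4.8) / (6 - 4.8)² = 67.3 per arm (stated: 67).

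Inflating for 7 clusters per arm, ICC 0.05 and cluster-size CV 0.60:

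m = 67 × 0.95 / (7 - 67 × 0.05 × 1.36) = 26.04 per cluster; 7 × 26.04 = 182.3 per arm (stated: 183).

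The plan's figures reproduce, and 6 is the only rate in them. The 6.82 and 7.17 are supporting citations.

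**2. Single-band gap with no education effect.** Apparent change = (age-specific rate / historical rate) - 1, on the lead-system bands:

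| Rate if STE does nothing | vs 6 | vs 6.82 | vs 7.17 |
|---|---|---|---|
| 2.1 (16-18) | -65% | -69% | -71% |
| 4.2 (19-21) | -30% | -38% | -41% |
| 5.3 (21-25) | -12% | -22% | -26% |

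The choice of comparator alone moves the oldest band from -12% to -26%.

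**3. Weighting over follow-up.** No participant stays at the youngest rate throughout, so I used

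rate = (p × younger rate + 24 × older rate) / (p + 24), with p = 6 or 12 pediatric months.

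Example: lead system 2.1 then 4.2, p = 12: (25.2 + 100.8) / 36 = 3.50; 3.50 / 6 - 1 = -42%.

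| Source (younger, older rate) | p = 6 | p = 12 | Change vs 6 |
|---|---|---|---|
| Lead system 2.1, 4.2 | 3.78 | 3.50 | -37%, -42% |
| Lead system 2.1, 5.3 | 4.66 | 4.23 | -22%, -29% |
| Lead system 4.2, 5.3 | 5.08 | 4.93 | -15%, -18% |
| Eight states 2.04, 3.61 | 3.30 | 3.09 | -45%, -49% |
| Georgia 0.8, 3.0 | 2.56 | 2.27 | -57%, -62% |
| North Carolina 5, 12 | 10.6 | 9.67 | +77%, +61% |

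Ten of the twelve values are at or beyond 20% in size; the exceptions are -15% and -18%. Against 7.17, the lead-system range becomes -29% to -51% and the North Carolina range +35% to +48%.

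**4. Lead-system consistency.** 1972 / 295 = 6.68 (emergency visits only). (1972 + 221) / 295 = 2193 / 295 = 7.43 (with admissions). Neither is 6.82. Any weighted mean of 2.1, 4.2 and 5.3 is at most 5.3, so sections 1.1 and 10.2 disagree for the same health system.

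**The case against.** A reader might infer that the comparison is bound to show a large benefit even if education does nothing, because the historical rates come from older or broader populations. The documents do not support that.

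- **Direction.** The North Carolina rates share their source with the 6. With most follow-up in adult care, they imply apparent harm under no effect.
- **Visit definition.** The lead-system average is described through emergency visits and admissions. The trial endpoint (10.3.1) also counts urgent care, day hospital and infusion visits. That raises the STE rate and so shrinks or reverses a spurious benefit. The definitions behind 6 and 7.17 are not given.
- **Population.** Only 7.17 is clearly from a different age range (18-30). The 6 and 6.82 are both labelled as emerging-adult figures, though neither is stated to be limited to pediatric-programme patients.
- **Size.** The 65% gap needs the whole arm to stay at the 16-18 rate throughout.
- **Status.** The plan admits the historical design and speaks only of potential impact. The randomised contrast does not use this comparison.

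All of this stands against a claim of certain benefit. None of it rescues the comparison: a null result that can fall on either side of zero, depending on which of the protocol's own sources applies, says nothing reliable about education.

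Simple repairs also fall short. The pre-enrolment year is expected to be pediatric care, so a before-after contrast over all follow-up mixes any STE effect with transfer and ageing. Standardising to the lead-system bands would rest on figures that conflict with section 10.2, on bands that overlap at age 21, and on visit types that are not itemised.

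**Conclusion.** The concern holds in this form: the planned comparison cannot separate an education effect from differences in age, care setting, region, period and visit definition. On the protocol's own rates, zero effect would appear as anything from about -62% to +77% against 6, mostly at or beyond the 20% the trial was designed to detect. A guaranteed spurious benefit is not supported.

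The ranges assume that a participant moves from the younger to the older published rate at transfer, with 6 or 12 pediatric and 24 adult months. The age mix of enrollees is not given, and the published age bands do not match the trial's exactly. The conclusion does not depend on any one path, because the sources disagree in sign. The plan should be changed, since this affects what may be concluded about structured education. It does not affect the randomised STE+PM versus STE comparison.

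**What to change.** 1. In 10.5.4, remove the claim that the historical comparison gives preliminary evidence of impact, and label it descriptive.
2. Report STE-arm rates by age band and separately for pediatric and adult follow-up, beside the full set of age-specific rates in 1.1 and 10.2, not only 6 to 7.17.
3. Where a historical source counts only emergency visits and admissions, restrict the STE rate to those types for that comparison. Section 6.4 lists emergency and urgent care together, so confirm first that the database separates them.
4. Add a descriptive comparison of the pediatric follow-up months with the same participants' 12-month pre-enrolment rate, which is already collected. State that regression to the mean remains, and that an STE effect in adult care cannot be separated from transfer and ageing.
5. Reconcile the lead-system figures in 1.1 and 10.2: the source of 6.82, the visit types counted, and why the age-band means lie below it.

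The cost is minor wording and a small amount of extra tabulation on data already planned. The price is a weaker statement about structured education.
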